5.1.3 Previous and Concomitant Treatment (Medication and Nonmedication Therapy)

Medications taken within 14 days before the Screening visit and up to the 30-Day Follow-up visit will be documented on the appropriate case report form.

Prior and concomitant medications include all vitamins, herbal remedies, over the counter, and prescription medications.

Subject with viral etiology (HCV, HBV) should be on stable doses of antiviral therapy at the time of study entry, if the Investigator feels these are of benefit to the subject. The Investigator should consult with Medical Monitor if initiation of antiviral therapy is deemed necessary during the study.

Concomitant use of enzalutamide with drugs with a narrow therapeutic index that are metabolized by CYP3A4 (e.g., alfentanil, cyclosporine, dihydroergotamine, ergotamine, fentanyl, pimozide, quinidine, sirolimus, tacrolimus), CYP2C9 (e.g., phenytoin, warfarin) and CYP2C19 (e.g., S-mephenytoin) should be avoided if possible as enzalutamide may

decrease their exposure. If coadministration with warfarin cannot be avoided, additional INR monitoring should be conducted.

Coadministration of enzalutamide with strong CYP2C8 inhibitors should be avoided. If coadministration of enzalutamide with strong CYP2C8 inhibitors cannot be avoided, the enzalutamide dose should be reduced to 80 mg/day. If coadministration of the strong inhibitor is discontinued, the enzalutamide dose should be returned to the dose used before initiation of the strong CYP2C8 inhibitor.

Subject should avoid use of any herbal medications or dietary supplements including products containing *Hypericum perforatum* (e.g., St. John's wort).

The following medications or therapies are prohibited during the receipt of study drug:

- Medications, including herbal therapies, with an antitumor effect
- Any investigational agent
- AR antagonists (e.g., bicalutamide, flutamide, nilutamide), however, spironolactone initiation during the study is allowed after Medical Monitor consultation
- 5- α reductase inhibitors (e.g., finasteride, dutasteride)
- Systemic androgens and estrogens (vaginal estrogen creams are allowed)

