5 TREATMENTS AND EVALUATION

5.1 Dosing and Administration of Study Drug(s) and Other Medication(s)

5.1.1 Dose/Dose Regimen and Administration Period

Eligible subjects will receive enzalutamide 160 mg/day (4 x 40 mg capsules) or placebo until disease progression, unacceptable toxicity, or any other discontinuation criteria are met. Best supportive care will be given to all subjects in addition to study drug. Best supportive care may include medications and supportive measures deemed necessary per Investigator's discretion to palliate disease-related symptoms and improve quality of life. Subjects on strong CYP2C8 (e.g., gemfibrozil) inhibitor should start study drug at 80mg/day after consultation with the Medical Monitor, if coadministration cannot be avoided.

Study drug will be self-administered at home by the subject, except for visit days where pharmacokinetic samples are collected. On visit days with pharmacokinetic sampling, study drug will be administered in clinic after the pharmacokinetic sample is collected. Subjects will keep a diary to record the date and time of study drug dose on the 2 days before pharmacokinetic visit days.

Subjects should not make up missed or vomited doses; dosing should resume on the next calendar day unless otherwise instructed. For the purposes of this study, a “missed dose” is considered a dose not administered within 4 hours of the regular dosing time.

Subjects may take study drug with or without food. Subjects must swallow capsules whole. Study drug may not be chewed, dissolved or capsules opened.

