5.1.2 Increase or Reduction in Dose of the Study Drug(s)

During the study, study drug treatment may be interrupted for individual subjects who experience a NCI CTCAE Grade ≥ 3 AE (except LFT AEs) that is attributed to the study drug and cannot be ameliorated with appropriate medical intervention. Study drug may be resumed at the original dose (160 mg/day) or at a reduced dose (120 mg/day or 80 mg/day), after discussion with and approval by the Medical Monitor. Treatment interruption for > 2 weeks must also be discussed with the Medical Monitor. The Sponsor may make a decision to change the dose based on recommendation from the DSMB’s safety review.

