5.1.2.1 Dose Modification Plan for LFT Changes

Study drug dosing should be interrupted if a subject experiences clinically significant liver toxicity related to study drug (\geq Baseline + 4 x ULN to < 20 x ULN for AST and ALT; grade 3 TBL). Testing should be repeated at Investigator’s discretion but at a minimum weekly to ensure that the subject’s LFT’s are returning to acceptable levels. If the subject’s toxicity resolves within 14 days to either \leq grade 1 (if normal at baseline) or no more than 1 grade above baseline (but no higher than grade 2), study drug may be reintroduced at a dose of 120 mg/day in consultation with the Medical Monitor. If the toxicity has not resolved within 14 days (as defined by either \leq grade 1 or no more than 1 grade above screening but no higher than grade 2), then the Medical Monitor must be consulted to determine if further interruption is permitted.

If any drug-related liver toxicity requiring dose interruption recurs or develops despite the initial dose reduction to 120 mg/day, the LFT monitoring instructions above should be followed and the study drug may be reintroduced at a dose of 80 mg/day. If any drug-related liver toxicity recurs at the reduced dose of 80 mg/day, the study drug should be discontinued.

Study drug must be discontinued for subjects with study drug related grade 4 LFTs (AST, ALT and TBL).

Table 2 Dose Modification Table for Drug-Related Liver Toxicities

NCI CTCAE V4.03	Dose Interruption	Dose Reduction
Grade 1 (AST, ALT, TBL)	No Change	No Change
Grade 2 to < Baseline + 4 x ULN (AST and ALT)	No Change	No Change
Grade 2 (TBL)	No Change	No Change
≥ Baseline + 4 x ULN and below 20 x ULN (AST and ALT)	Hold until grade 1 or, if event was grade 1 or 2 at screening, until returns to grade 2 or lower. If it takes over 14 days to reduce toxicity to acceptable levels then the MM should be consulted	1st episode – reduce to 120 mg/ day 2nd episode – reduce to 80 mg/day 3rd episode – Discontinue treatment
Grade 3 (TBL)	Hold until grade 1 or, if event was grade 2 at screening, until returns to grade 2 or lower. If it takes over 14 days to reduce toxicity to acceptable levels then the MM should be consulted	1st episode – reduce to 120 mg/day 2nd episode – reduce to 80 mg/day 3rd episode – Discontinue treatment
Grade 4 (AST, ALT, TBL)	Discontinue Treatment	Discontinue Treatment

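### The flat 80 mg/day rule for strong CYP2C8 inhibitors offsets the interaction only from 160 mg/day; in a toxicity-reduced subject it permits about full-dose exposure with no required Medical Monitor contact

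*Protocol*

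**What the plan says.** **Inhibitor rule.** Protocol 5.1.3 first tells sites to avoid strong CYP2C8 inhibitors. If that is not possible: "If coadministration of enzalutamide with strong CYP2C8 inhibitors cannot be avoided, the enzalutamide dose should be reduced to 80 mg/day". The Synopsis and Appendix 12.1 carry the same sentence. It does not refer to the subject's current dose. When the inhibitor is stopped, "the enzalutamide dose should be returned to the dose used before initiation of the strong CYP2C8 inhibitor".

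**Toxicity reductions.** Under 5.1.2, after an attributed Grade 3 or higher event other than a liver-test event, dosing may resume at 160 mg/day "or at a reduced dose (120 mg/day or 80 mg/day), after discussion with and approval by the Medical Monitor". Under 5.1.2.1, after a first liver episode, "study drug may be reintroduced at a dose of 120 mg/day in consultation with the Medical Monitor". A second episode leads to 80 mg/day. After that: "If any drug-related liver toxicity recurs at the reduced dose of 80 mg/day, the study drug should be discontinued". Neither section mentions inhibitors.

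**Medical Monitor contact about an inhibitor.** Section 5.1.1 says that subjects already on a strong CYP2C8 inhibitor "should start study drug at 80mg/day after consultation with the Medical Monitor, if coadministration cannot be avoided". Section 5.1.3 has no matching step for an inhibitor added during treatment. It does have one for other drugs: "The Investigator should consult with Medical Monitor if initiation of antiviral therapy is deemed necessary during the study". Starting spironolactone on study also needs consultation.

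**Open-label period.** Appendix 12.9 keeps reduced subjects on their reduced dose and refers back to 5.1.3 and Appendix 12.1, so the text still applies.

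**The concern.** A fixed target dose works as an interaction adjustment only from one starting dose. Here that is 160 mg/day. Subjects on 120 or 80 mg/day are there because they were judged not to tolerate more. If an inhibitor is added and 5.1.3 is followed, their exposure can return to about the level from which they were reduced. For liver toxicity, 80 mg/day is also the last step before permanent discontinuation.

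The case would not show up elsewhere as an irregularity. Section 5.5.9 defines overdose by dose above 160 mg once daily, and a site that follows 5.1.3 has not deviated under 8.1.6. What is at stake is the safety of individual subjects.

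There is a smaller wording gap. The return sentence preserves a toxicity reduction made before the inhibitor. It does not say what governs if a reduction is made while the inhibitor is being given.

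**Working it through.** **Inputs**
- Interaction: composite AUC (enzalutamide plus active metabolite) rises 2.2-fold with gemfibrozil in healthy subjects (Protocol 1.2.2.1).
- Approximate dose proportionality at steady state, 30 to 360 mg/day, reported with the data in patients with castration-resistant prostate cancer (1.2.2.1).
- Dose levels 160, 120 and 80 mg/day (5.1.1, 5.1.2, 5.1.2.1); capsule strength 40 mg (4.1.1).

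**Assumption.** Both pharmacokinetic statements carry over to subjects with hepatocellular carcinoma. The documents give no interaction data in that population.

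**Reproducing the protocol's 80 mg.** The dose that matches 160 mg without an inhibitor is 160 / 2.2 = 72.7 mg. The nearest multiple of a 40 mg capsule is 80 mg. The rule is therefore right for a subject on 160 mg/day.

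**Applying it to each starting dose.** With the inhibitor, 80 mg acts like 80 × 2.2 = 176 mg. Relative to full dose this is 176 / 160 = 1.10.

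| Dose before inhibitor | Dose under 5.1.3 | Exposure before (× full dose) | Exposure with inhibitor (× full dose) | Change |
|---|---|---|---|---|
| 160 mg | 80 mg | 160/160 = 1.00 | 1.10 | 176/160 = 1.10 |
| 120 mg | 80 mg | 120/160 = 0.75 | 1.10 | 176/120 = 1.47 |
| 80 mg | 80 mg | 80/160 = 0.50 | 1.10 | 176/80 = 2.20 |

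**How far this depends on the 2.2.**
- Exposure rises from 120 mg if the ratio exceeds 120/80 = 1.5.
- Exposure rises from 80 mg if the ratio exceeds 80/80 = 1.0.
- The reduction is fully cancelled only if the ratio is at least 160/80 = 2.0.

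Over an assumed ratio range of 1.8 to 2.6 (not from the documents), 80 mg with the inhibitor gives 80 × 1.8 / 160 = 0.90 to 80 × 2.6 / 160 = 1.30 times full-dose exposure. At 1.8 the reduction is only partly lost: (144 − 120)/(160 − 120) = 60% of a cut to 120 mg, and (144 − 80)/(160 − 80) = 80% of a cut to 80 mg.

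**Matching doses for reduced subjects.** 120 / 2.2 = 54.5 mg and 80 / 2.2 = 36.4 mg. With 40 mg capsules the nearest dose is 40 mg in both cases, giving 40 × 2.2 = 88 mg-equivalents. That is 0.73 of the exposure at 120 mg and 1.10 of that at 80 mg. The protocol has no 40 mg/day level.

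**The case against.** Several points on the other side stand.

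- **The rule does reach subjects on 120 mg/day.** It takes them to 80 mg; the fault is that the step is too small. A reader might infer that the protocol is silent on all reduced subjects, but the text does not support that. At 80 mg/day an instruction to reduce to 80 mg cannot be carried out, so the rise follows from what the text leaves unsaid, and the advice to avoid inhibitors is the guidance that remains.
- **The Medical Monitor is not absent.** The toxicity reduction itself generally involves the Medical Monitor (5.1.2, 5.1.2.1). Concomitant medications and laboratory tests are collected at each treatment visit, and stopping rules apply. A reader might infer that such subjects go unwatched; they do not. What is missing is contact about the inhibitor before it starts. Laboratory tests react only afterwards. Visits settle at every 4 weeks in the double-blind period and every 8 weeks in the open-label period, while steady state is reached by day 28 (1.2.2.1).
- **Harm is not shown.** The protocol accepts the same 1.10 level in a subject who tolerates 160 mg/day. The level lies within the 30 to 360 mg/day range, and individual daily doses up to 600 mg have been given. Section 1.2.1.3 reports no evidence of hepatotoxicity in animals or in the clinical program. A reader might infer a dangerous new exposure; the documents do not support that. The point is only that a reduction made for toxicity is undone.
- **The case is probably rare.** It needs toxicity, a reduction, continued treatment and then an unavoidable inhibitor. Only gemfibrozil is named, although Appendix 12.1 points to an external list. Placebo subjects, about one third under 2:1 randomization, cannot be affected. All 165 subjects are enrolled and the primary analysis is done, so the number who could still benefit is not given and may be zero.

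**Conclusion.** The point holds as a minor one. The flat 80 mg/day rule is correct from 160 mg/day. For an enzalutamide subject already reduced for toxicity it allows exposure to rise 1.47-fold (from 120 mg) or 2.2-fold (from 80 mg), to about 1.10 times full-dose exposure. The protocol asks for no Medical Monitor contact when the inhibitor is added on study. The size rests on the healthy-subject gemfibrozil ratio and on dose proportionality carrying over. The direction is firmer, since it needs only a ratio above 1.5 or 1.0 respectively.

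A reader might infer some effect on the efficacy result. The documents give no support for that: overall survival is analyzed in all randomized subjects, and nothing in its definition or test depends on this rule. Existing visit tests and stopping rules give partial protection. The change is worth making mainly because it is cheap and extends a safeguard that 5.1.1 already contains.

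**What to change.** In Protocol 5.1.3 and its copies in the Synopsis and Appendix 12.1:

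1. State that the flat 80 mg/day rule is for subjects taking 160 mg/day.
2. Require Medical Monitor consultation on the study-drug dose, including whether to hold it, before a strong CYP2C8 inhibitor is started in a subject whose dose was reduced for toxicity. This wording leaves out subjects who are below 160 mg/day only because of the inhibitor.
3. State that the dose after the inhibitor stops must respect any toxicity reduction made before or during coadministration.

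A default hold and a 40 mg/day level are options for the sponsor, not part of this fix. A hold during long-term inhibitor use could come close to ending treatment. The existing sentence "Treatment interruption for > 2 weeks must also be discussed with the Medical Monitor" sits in a paragraph on adverse-event interruptions, so its use for inhibitor holds would need to be stated. A 40 mg/day level would add a dose below the lowest one in the protocol.

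**Cost.** Three sentences in three places. They bear on subject safety, so section 8.3.3 calls for IRB/IEC approval before they are implemented; they could go into the next amendment. The running cost is a small amount of Medical Monitor time.

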5.1.4 Treatment Compliance

Study subjects should be counseled on the need to meet 100% compliance with study drug. The Investigator or designee should ensure that study subjects meet this goal throughout the study period.

Treatment compliance should be monitored closely as sites will perform accountability of study drug doses dispensed and returned and deviation in overall compliance < 80% should be reported to the Sponsor.

5.2 Demographics and Baseline Characteristics

5.2.1 Demographics

Demographic information will be collected at Screening for all subjects and will include age or date of birth, sex, race, ethnicity (as local regulations allow) and history of smoking and alcohol use.

5.2.2 Medical History

Medical history includes all significant medical conditions that have occurred or are currently ongoing at the time of consent. The condition, onset date, and recovery date will be collected. NCI CTCAE grade will be collected for conditions that are ongoing at the time of consent.

5.2.3 Diagnosis of the Target Disease, Severity and Duration of Disease

Diagnosis of advanced HCC will be captured including dates of diagnosis, etiology and the presence/absence of cirrhosis. Prior systemic treatment for advance HCC with sorafenib or other anti-VEGF therapy and confirmed disease progression or discontinuation of sorafenib

due to intolerance will also be collected. BCLC stage (Appendix 12.4) and the Child-Pugh class status (Appendix 12.5) will be documented during Screening.

5.3 Efficacy and Pharmacodynamics Assessments

5.3.1 Efficacy Assessment

5.3.1.1 Survival Status and Subsequent Therapies

Subjects who are alive after the completion of the 30-day Follow-up Visit will continue to be contacted by site personnel for long-term survival follow-up every 30 days. This assessment may be conducted by telephone if the subject is unable to travel. Information on survival status and subsequent therapies will be obtained. Follow-up will continue for up to 2 years after the 30-day Follow-up Visit or until the final analysis.

5.3.1.2 Radiographic Assessment

Disease response and progression will be evaluated in this study using the RECIST criteria (version 1.1, 2009) and assessed by the Investigator. Radiographic imaging technique will be performed using either diagnostic CT scan or MRI with contrast.

Imaging may be performed at any time to confirm suspected progression of disease. Assessment will include tumor measurements for target lesions, nontarget lesions and assessment for any new lesions. An overall assessment will be characterized for each time point evaluation. At the end of study for that subject, the overall best response to the study regimen will be characterized. Refer to Appendix 12.7 RECIST v1.1 for additional details.

Baseline imaging performed prior to informed consent may be used so long as it is performed within 28 days prior to Day 1. Subsequent scans including chest/abdominal/pelvic imaging will be done every 8 weeks (\pm 7 days) from Day 1 until disease progression or other discontinuation criterion is met. Scans should be done every 8 weeks regardless of treatment interruption or delays. To ensure comparability, the radiology/scans throughout the study should be performed using identical techniques (e.g., scans performed immediately following bolus contrast administration should be made with a standard volume of contrast, the identical contrast agent and preferably the same scanner). The same method should be employed and assessed by the same individual on each occasion, when possible.

[REDACTED]

[REDACTED]

[REDACTED]

[REDACTED]

[REDACTED]

[REDACTED]

[REDACTED]

5.3.2.3 [REDACTED]

[REDACTED]

5.4 Safety Assessment

5.4.1 Height and Weight

Height and weight will be measured using standard institution practice and equipment.

5.4.2 Vital Signs

Vital signs will include systolic and diastolic blood pressure (mmHg), radial pulse (beats/min) and temperature. All vital signs will be measured with the subject in the sitting or supine position.

5.4.3 Adverse Events

All observed or spontaneously reported AEs will be documented within the source. The Investigator will avoid asking leading questions to influence the reporting of AEs.

AE collection will begin at the time the informed consent form (ICF) is signed and continue through to 30 days after the last dose date of study drug or initiation of a new antineoplastic or new investigational agent, whichever comes first.

See Section [5.5](#) Adverse Events and Other Safety Aspects for information regarding AE collection and data handling.

5.4.4 Laboratory Assessments

Routine laboratory samples for hematology, chemistry, coagulation, viral load (if applicable), pregnancy and urinalysis will be collected and analyzed at the Institution's local laboratory. The local laboratory must be accredited to perform the protocol required tests and a certificate of accreditation and laboratory normal ranges must be provided to the Sponsor. Please refer to Appendix 12.8 Laboratory Assessments for a listing of analytes to be assessed.

5.4.5 Physical Examination

Standard, full physical examinations will be performed at Screening and Day 1 to assess general appearance, skin, eyes, ears, nose, throat neck, cardiovascular, chest and lungs, abdomen, musculoskeletal, neurologic status, mental status, and lymphatic systems. Genitourinary and rectal system examinations are to be performed only if clinically indicated. After Day 1, a brief symptom directed physical examination may be performed.

New or worsening clinically significant findings on physical exam will be recorded as AEs if they meet the criteria in Section 5.5.1 Definition of Adverse Events.

5.4.6 Electrocardiogram (ECG)

A 12-lead ECG will be performed on all subjects at the Institution and interpreted by the Institution's medically trained staff. Parameters that include heart rate, PR interval, RR interval, QRS interval, QT interval will be collected. Abnormalities and clinical significance as judged by the Investigator will be reported as well. It is recommended that ECG reports are printed in duplicate and photocopied to prevent fading.

ECG should be obtained after the subject has rested quietly and is awake in a fully supine position or semi-recumbent, if supine not tolerated) for 10 minutes.

All on-treatment ECGs will be obtained prior to drug administration. Whenever a study procedure coincides with the scheduled time point for an ECG, the study activities are ideally undertaken in a fixed sequence: ECG first, vital signs.

5.5 Adverse Events and Other Safety Aspects

5.5.1 Definition of Adverse Events (AEs)

AEs will be collected from the time of consent until 30 days after the last dose of study drug or initiation of a new antineoplastic or new investigational agent, whichever comes first. An AE is defined as any untoward medical occurrence in a subject administered a study drug or has undergone study procedures and which does not necessarily have a causal relationship with this treatment. An AE can therefore be any unintended sign (including an abnormal laboratory finding), symptom, or disease temporally associated with the use of a study drug, whether or not related to the study drug.

Some countries may have additional local requirements for events that are required to be reported as AEs or in an expedited manner similar to an SAE. In these cases, it is the

Investigator's responsibility to ensure that these AEs or other reporting requirements are followed and the information is appropriately recorded in the source data accordingly.

Adverse events are events that begin or worsen from the time of informed consent through the 30-day Follow-up Period or initiation of a new antineoplastic or new investigational agent, whichever comes first. Treatment-emergent AEs (TEAEs) are events that begin or worsen from the date of first study drug administration through the 30-day Follow-up Period or initiation of new treatment, whichever comes first.

An abnormality identified during a medical test (e.g., laboratory parameter, vital sign, ECG data, physical exam) should be defined as an AE only if the abnormality meets one of the following criteria:

- Induces clinical signs or symptoms
- Requires active intervention
- Requires interruption or discontinuation of study medication
- The abnormality or investigational value is clinically significant in the opinion of the Investigator.

